- g: ECHO or MUGA to be performed at screening and again on C1D28 (acceptable window C1 D23-D29.) Thereafter, exam should be repeated every 12 weeks (+/-1 week.) The same modality used during screening should be used for all follow up exams.
- h: Tumor measurements and radiologic evaluation should occur every 8 weeks +/- 1 week. If a patient is on a dose hold, scans should be kept on original schedule and should not be shifted. Patients that have scans which reveal disease progression do not need to repeat end of treatment scans.
- i: Serum pregnancy test (women of childbearing potential) must be done within 7 days of C1D1.
- j: Tumor biopsies to be performed only in first 15 patients enrolled in Part 2.
- k: Pre-study tumor biopsy to occur between days -21 and day-1. When possible, it is preferred, but not required, that the pre-treatment biopsy be performed between days -7 and -1 of treatment in order to most accurately represent the baseline signaling activity prior to treatment. Platelet count and PT/PTT must be checked prior to procedure according to institutional guidelines, and must be in acceptable range as defined in section 9.1.1.2.
- 1: On treatment biopsy to occur ~2 weeks after trametinib dosing on C1D22 (+/- 7 days.) Platelet count and PT/PTT must be checked prior to procedure on the same day, and must be in acceptable range as defined in section 9.1.1.2.
- m: Complete PK schedule detailed in Section 9.3. Additional PK samples (single trough measurements only) required on day 1 of cycles 4, 8, and 12, not represented on this calendar.
- n: Single pre-dose (pre-trametinib and navitoclax) trough on C2D1.
- o: At least 20 unstained slides are required. If a patient is having a tumor biopsy, less than 20 is acceptable with PI approval.
- p: Off study procedures should be performed within 14 days of last dose. Patients will be followed until the resolution or stabilization of all study-related toxicity and for a minimum of 30 days after removal from study or until death, whichever occurs first. Patients removed from study for unacceptable adverse event(s) will be followed until resolution or stabilization of the adverse event.

Part 2 (Phase 2) Schedule B (To be used if RP2D is to be given by Schedule B)

	Pre- Study	C1D1	C1D8	C1D15	C1D22	C2D1	C2D15	C3D1, C4D1, etc	Off Study ^p	
Trametinib		T	Т	T	T	Т	Т	Т		
Navitoclax		L	N	N	N	N	N	N		
Informed consent a	X									
Demographics	X									
Medical history	X									
Concurrent meds	X	X						X		
Physical exam ^b	X	X	X	X	X	X	X	X	X	
Vital signs ^c	X	X	X	X	X	X	X	X	X	
Height	X									
Weight	X	X	X	X	X	X	X	X	X	
Performance status	X	X	X	X	X	X	X	X	X	
CBC w/diff, plts	X	X	X	X	X	X	X	X	X	
Serum chemistry ^d	X	X	X	X	X	X	X	X	X	
PT/PTT	X	X	X	X		X		X	X	
Tumor Markers ^e	X					X		X		
Urinalysis	X									
EKG ^f	X	X	X	X	X	X	X			
Echocardiogram or MUGA	X	Repe	Repeat on C1D28 (up to 5 days prior or on C2D1.) Thereafter, repeat every 12 weeks (use same methodology for baseline and follow up). g							
Ophthalmology exam	X		Repeated as needed only if patient experiences vision changes							

100

Adverse event evaluation		X						X	X		
Radiologic Evaluations/Tumor measurements	X	followin Docume	Radiologic measurements (by CT or MRI) should be performed every 8 weeks ollowing Cycle 1 Day 1. Tumor measurements are repeated every 8 weeks. Documentation (radiologic) must be provided for patients removed from study for rogressive disease. h								
B-HCG	Xi										
Tumor biopsy	X ^{j,k}			$X^{j,l}$							
PK blood draw ^m						Xn		X ^m			
Archival Tissue	Xº										

- T: Trametinib. Dose as assigned; dose first in morning on empty stomach, at least 1 hour before food (there are no hematologic paramaters that must be met to continue dosing with trametinib at the beginning of each cycle.)
- N: Navitoclax. Dose as assigned; dose second in morning with food, at least 1 hour after trametinib
- L: Lead-in dose of navitoclax. 150 mg daily in morning for 7 days, dosed as above.
- a: Informed consent can be signed within 28 days of C1D1.
- b: Complete physical exam required pre-study and on Day 1 of each cycle, including head, eye, ear, nose, throat (HEENT,) cardiovascular, dermatological, musculoskeletal, respiratory, gastrointestinal, and neurological systems. Limited or symptom directed physical exam at the discretion of the investigator is sufficient at all other visits.
- c: Vitals should include blood pressure, heart rate, respiratory rate, oxygen saturation, and temperature.
- d: Albumin, alkaline phosphatase, total bilirubin, bicarbonate, BUN, calcium, chloride, creatinine, glucose, LDH, phosphorus, potassium, total protein, SGOT [AST], SGPT [ALT], sodium.
- e: Disease-specific tumor markers as appropriate (e.g. CEA, CA-19-9, CA125) should be drawn at specified times provided the patient has elevation of that specific tumor maker prior to study enrollment. Colorectal: CEA; Pancreatic: CEA and CA-19-9; Lung: CEA; Any other tumor types: PI with treating MD can advise which tumor markers are appropriate to follow.
- f: EKGs should be done pre-dose at all required time points.
- g: ECHO or MUGA to be performed at screening and again on C1D28 (acceptable window C1 D23-D29.) Thereafter, exam should be repeated every 12 weeks (+/-1 week.) The same modality used during screening should be used for all follow up exams.
- h: Tumor measurements and radiologic evaluation should occur every 8 weeks +/- 1 week. If a patient is on a dose hold, scans should be kept on original schedule and should not be shifted. Patients that have scans which reveal disease progression do not need to repeat end of treatment scans.
- i: Serum pregnancy test (women of childbearing potential) must be done within 7 days of C1D1.
- j: Tumor biopsies to be performed only in first 15 patients enrolled in Part 2.
- k: Pre-study tumor biopsy to occur between day -21 and day -1. When possible, it is preferred, but not required, that the pre-treatment biopsy be performed between days -7 and -1 of treatment in order to most accurately represent the baseline signaling activity prior to treatment. Platelet count and PT/PTT must be checked prior to procedure according to institutional guidelines, and must be in acceptable range as defined in section 9.1.1.3.
- 1: On-treatment tumor biopsy to occur after ~14 days of trametinib dosing on day 15 (+/- 7 days). Platelet count and PT/PTT must be checked prior to procedure on same day, and must be in acceptable range as defined in section 9.1.1.3.
- m: Complete PK schedule detailed in Section 9.3. Additional PK samples (single trough measurement only) required on day 1 of cycles 4, 8, and 12, not represented on this calendar
- n: Single pre-dose (pre-trametinib and navitoclax) trough on C2D1. See Section 9.3 for details.
- o: At least 20 unstained slides are required. If a patient is having a tumor biopsy, less than 20 is acceptable with PI approval.
- p: Off study procedures should be performed within 14 days of last dose. Patients will be followed until the resolution or stabilization of all study-related toxicity and for a minimum of 30 days after removal from study or until death, whichever occurs first. Patients removed from study for unacceptable adverse event(s) will be followed until resolution or stabilization of the adverse event.

Part 2 (Phase 2) Schedule C (To be used if RP2D is to be given by Schedule C)

	Pre- Study	C1D1	C1D8	C1D15	C1D22	C2D1	C2D15	C3D1, C4D1, etc	Off Study ^p
Trametinib		Т	Т			Т		Т	
Navitoclax		L	N	N	N	N	N	N	
Informed consent a	X								
Demographics	X								
Medical history	X								
Concurrent meds	X	X						X	
Physical exam ^b	X	X	X	X	X	X	X	X	X
Vital signs ^c	X	X	X	X	X	X	X	X	X
Height	X								
Weight	X	X	X	X	X	X	X	X	X
Performance status	X	X	X	X	X	X	X	X	X
CBC w/diff, plts	X	X	X	X	X	X	X	X	X
Serum chemistry ^d	X	X	X	X	X	X	X	X	X
PT/PTT	X	X	X	X		X		X	X
Tumor Markers ^e	X					X		X	
Urinalysis	X								
EKG ^f	X	X	X	X	X	X	X		
Echocardiogram or MUGA	X	Repe						after, repeat every 12 ollow up). g	

102

Ophthalmology exam	X	I	Repeated as needed only if patient experiences vision changes									
Adverse event evaluation		X	XX									
Radiologic Evaluations/Tumor measurements	X	following C Documentat	adiologic measurements (by CT or MRI) should be performed every 8 weeks llowing Cycle 1 Day 1. Tumor measurements are repeated every 8 weeks. ocumentation (radiologic) must be provided for patients removed from study for ogressive disease. h									
B-HCG	Xi											
Tumor biopsy	$X^{j,k}$		$X^{j,l}$									
PK blood draw ^m					Xn		X ^m					
Archival Tissue	Xº											
cfDNA blood draw		X			X		X					

- T: Trametinib. Dose as assigned; dose in evening on empty stomach, at least 1 hour before or two hours after food (there are no hematologic paramaters that must be met to continue dosing with trametinib at the beginning of each cycle.)
- N: Navitoclax. Dose as assigned; dose in morning with food
- L: Lead-in dose of navitoclax. 150 mg daily in morning for 7 days, dosed as above.
- a: Informed consent can be signed within 28 days of C1D1.
- b: Complete physical exam required pre-study and on Day 1 of each cycle, including head, eye, ear, nose, throat (HEENT,) cardiovascular, dermatological, musculoskeletal, respiratory, gastrointestinal, and neurological systems. Limited or symptom directed physical exam at the discretion of the investigator is sufficient at all other visits.
- c: Vitals should include blood pressure, heart rate, respiratory rate, oxygen saturation, and temperature.
- d: Albumin, alkaline phosphatase, total bilirubin, bicarbonate, BUN, calcium, chloride, creatinine, glucose, LDH, phosphorus, potassium, total protein, SGOT [AST], SGPT [ALT], sodium.
- e: Disease-specific tumor markers as appropriate (e.g. CEA, CA-19-9, CA125) should be drawn at specified times provided the patient has elevation of that specific tumor maker prior to study enrollment. GYN: CA-125; Pancreatic: CEA and CA-19-9; Lung: CEA; Any other tumor types: PI with treating MD can advise which tumor markers are appropriate to follow.
- f: EKGs should be done pre-dose at all required time points.
- g: ECHO or MUGA to be performed at screening and again on C1D28 (acceptable window C1 D23-D29.) Thereafter, exam should be repeated every 12 weeks (+/-1 week.) The same modality used during screening should be used for all follow up exams.
- h: Tumor measurements and radiologic evaluation should occur every 8 weeks +/- 1 week. If a patient is on a dose hold, scans should be kept on original schedule and should not be shifted. Patients that have scans which reveal disease progression do not need to repeat end of treatment scans
- i: Serum pregnancy test (women of childbearing potential) must be done within 7 days of C1D1.
- j: Tumor biopsies to be performed only in first 15 patients enrolled in Part 2.
- k: Pre-study tumor biopsy to occur between day -21 and day -1. When possible, it is preferred, but not required, that the pre-treatment biopsy be performed between days -7 and -1 of treatment in order to most accurately represent the baseline signaling activity prior to treatment. Platelet count and PT/PTT must be checked prior to procedure according to institutional guidelines, and must be in acceptable range as defined in section 9.1.1.3.
- l: On-treatment tumor biopsy to occur after ~14 days of trametinib dosing on day 15 (+/- 7 days). Platelet count and PT/PTT must be checked prior to procedure on same day, and must be in acceptable range as defined in section 9.1.1.3.
- m: Complete PK schedule detailed in Section 9.3. Additional PK samples (single trough measurement only) required on day 1 of cycles 4, 8, and 12, not represented on this calendar
- n: Single pre-dose (pre-navitoclax) trough on C2D1. See Section 9.3 for details.
- o: At least 20 unstained slides are required. If a patient is having a tumor biopsy, less than 20 is acceptable with PI approval.

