2.5 Correlative Studies Background

2.5.1 Pharmacokinetic Studies

While the pharmacokinetics of trametinib and navitoclax given as single agents is well-understood, this study will evaluate the pharmacokinetics of these agents when given in combination. During the Phase 1b portion of the study, subjects will have blood drawn pre-dose, and 2h, 4h, 6h, 8h, and 23h after dosing on (1) day 7 of a 7-day navitoclax single-agent lead-in dosing period and (2) again after 14 days of combination dosing. Pre-dose (0h) levels of trametinib and navitoclax will also be measured on day 1 of cycles 2, 4, 8 and 12. Plasma concentrations of trametinib will be determined through established procedures by GSK, and concentrations of navitoclax will be determined through established procedures by AbbVie. These studies will be used to determine whether trametinib and navitoclax interact from a pharmacokinetic standpoint, and will be used to determine the maximum observed plasma drug concentration (Cmax), area-under-the concentration-time-curve from zero (pre-dose) to 24 hours (AUC(0-24)), pre-dose (trough) drug concentration for trametinib and navitoclax, and t1/2. Since it is not yet clear whether the single-agent MTDs of these compounds can reached when these agents are dosed in combination, measuring the plasma drug concentrations achieved at

each dose level provide a valuable comparison of the drug exposure achieved at a given dose level to what is known to be achieved at the single-agent MTD.

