9.3.1.2.3 Schedule for PK sample collection for Part 1 (Phase 1b) Schedule C

Cycle (C), day (D)	Timing of PK sample blood draws	PK for
C1, D7	Pre-dose navitoclax (0h), 2h (+/-5 min,)	Navitoclax and
	4h (+/-5min,) 6h (+/-5 min,) 8h (+/-24	trametinib
	min)	
C1, D8	Pre-dose navitoclax (0h), (will represent	Navitoclax and
	24h post-dose from prior day)	trametinib
C1, D14 [#]	Pre-dose navitoclax (0h), 2h (+/- 5	Navitoclax and
	min,) 4h (+/-5 min,) 6h (+/- 5 min,) 8h	trametinib
	(+/- 24 min)	
C1, D15#	Pre-dose navitoclax (0h)	Navitoclax and
	(will represent 23h post-dose navitoclax	trametinib
	from prior day, +/- 1 hr)	
C2, D1	Pre-dose navitoclax (single trough	Navitoclax and
	level)	trametinib
C4, D1	Pre-dose navitoclax (single trough	Navitoclax and
	level)	trametinib
C8, D1	Pre-dose navitoclax (single trough	Navitoclax and
	level)	trametinib
C12, D1	Pre-dose navitoclax (single trough	Navitoclax and
	level)	trametinib

Version Date: July 22, 2022

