10. STUDY CALENDAR

Baseline evaluations are to be conducted within 2 weeks prior to start of protocol therapy. Scans and x-rays, Echocardiogram or MUGA, and ophthalmic examination must be done ≤ 4 weeks prior to the start of therapy. In the event that the patient's condition is deteriorating, laboratory evaluations should be repeated within 48 hours prior to initiation of the next cycle of therapy. All study visits have a ± -3 day window after Cycle 2, Day 1.

Labs obtained on C1, D1 must re-meet eligibility criteria.

[#] Represents 14th day of trametinib dosing under Schedule C Trametinib dosing is always in the evenings. Timing is not adjusted on PK days

Part 1 (Phase 1b) Schedule A

	Pre- Study	C1D1	C1D7	C1D8	C1D15	C1D21	C1D22	C2D1	C2D15	C3D1, C4D1, etc	Off Study ^q
Trametinib				T	T	T	T	T	T	Т	
Navitoclax		L	L	N	N	N	N	N	N	N	
Informed consent a	X										
Demographics	X										
Medical history	X										
Concurrent meds	X	X								X	
Physical exam b	X	X		X	X		X	X	X	X	X
Vital signs c	X	X	X	X	X	X	X	X	X	X	X
Height	X										
Weight	X	X		X	X		X	X	X	X	X
Performance status	X	X		X	X		X	X	X	X	X
CBC w/diff, plts	X	X	X		X		X	X	X	X	X
Serum chemistry ^d	X	X	X		X		X	X	X	X	X
PT/PTT	X	X	X				X			X	X
Tumor Markers ^e	X							X		X	X
Urinalysis	X										
EKG ^f	X	X		X	X		X	X	X		
Echocardiogram or MUGA	X	Repeat	on C1D28				l.) Thereaft ine and foll			reeks (use	
Ophthalmology exam	X		Rej	peated as	needed onl	y if patient	experience	s vision cl	hanges		
Adverse event evaluation		X								X	X
Radiologic evaluation/Tumor measurements	X	Cycle 1	Radiologic measurements (by CT or MRI) should be performed every 8 weeks following Cycle 1 Day 1. Tumor measurements are repeated every 8 weeks. Documentation (radiologic) must be provided for patients removed from study for progressive disease. h								
B-HCG i	X										

92

Version Date: July 22, 2022

Tumor biopsy	X j				Xk			
PK blood draw ^l		Xm	Xm	X ⁿ	Xn	Xº	X^{l}	
Archival Tissue	Xp							

- T: Trametinib. Dose as assigned; dose first in morning on empty stomach, at least 1 hour before food (there are no hematologic paramaters that must be met to continue dosing with trametinib at the beginning of each cycle.)
- N: Navitoclax. Dose as assigned; dose second in morning with food, at least 1 hour after trametinib
- L: Lead-in dose of navitoclax. 150 mg daily in morning for 7 days, dosed as above.
- a: Informed consent can be signed within 28 days of C1D1.

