- h: Tumor measurements and radiologic evaluation should occur every 8 weeks +/- 1 week. If a patient is on a dose hold, scans should be kept on original schedule and should not be shifted. Patients that have scans which reveal disease progression do not need to repeat end of treatment scans.
- i: Serum pregnancy test (women of childbearing potential) must be done within 7 days of C1D1.
- j: Pre-study tumor biopsy to occur between days -21 and day-1. When possible, it is preferred, but not required, that the pre-treatment biopsy be performed between days -7 and -1 of treatment in order to most accurately represent the baseline signaling activity prior to treatment. Platelet count and PT/PTT must be checked prior to procedure according to institutional guidelines and must be in acceptable range as defined in section 9.1.1.2.
- k: On treatment biopsy to occur ~2 weeks after trametinib dosing on day 15 (+/- 7 days.) Platelet count and PT/PTT must be checked prior to procedure on the same day, and must be in acceptable range as defined in section 9.1.1.2.
- 1: Complete PK schedule detailed in Section 9.3. Additional PK samples (single trough measurements only) required on day 1 of cycles 4, 8, and 12, not represented on this calendar.
- m: Includes pre-dose (0h), 2h, 4h, 6h, 8h draws on C1D7 and 24h draw (pre-dose) on C1D8. See section 9.3 for details.
- n: Includes pre navitoclax (0h), and 2h, 4h, 6h, 8h post navitoclax draws on C1D14 and 24h draw on C1D15. See section 9.3 for details.
- o: Single pre-dose (pre-navitoclax) trough on C2D1. See Section 9.3 for details.
- p: At least 20 unstained slides are required. If a patient is having a tumor biopsy, less than 20 is acceptable with PI approval.
- q: Off study procedures should be performed within 14 days of last dose. Patients will be followed until the resolution or stabilization of all study-related toxicity and for a minimum of 30 days after removal from study or until death, whichever occurs first. Patients removed from study for unacceptable adverse event(s) will be followed until resolution or stabilization of the adverse event.

Part 2 (Phase 2) Schedule A (To be used if RP2D is to be given by Schedule A)

	Pre- Study	C1D1	C1D8	C1D15	C1D22	C2D1	C2D15	C3D1, C4D1, etc	Off Study ^p
Trametinib			Т	T	T	Т	Т	T	
Navitoclax		L	N	N	N	N	N	N	
Informed consent a	X								
Demographics	X								
Medical history	X								
Concurrent meds	X	X						X	
Physical exam ^b	X	X	X	X	X	X	X	X	X

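### Under Schedule C the PK draws do not target the trametinib peak, and the day-1 samples are trametinib washout levels rather than end-of-interval troughs

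*Combined protocol and SAP*

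**What the plan says.** Section 5.1.1 and Table 5.2 define Schedule C as trametinib in the p.m. on days 1-14 of a 28-day cycle, with navitoclax in the a.m. on days 1-28. The footnote to the Schedule C PK table (9.3.1.2.3; in this copy it prints at the head of Section 10) reads: "Trametinib dosing is always in the evenings. Timing is not adjusted on PK days".

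That table ties every draw to navitoclax. The C1D7 and C1D14 sets start "Pre-dose navitoclax (0h), 2h (+/-5 min" and run to 8 h, with one more draw the next morning. The entry for day 1 of cycles 2, 4, 8 and 12 starts "Pre-dose navitoclax (single trough". Every row is marked for both drugs. The Part 1 Schedule C calendar agrees: "Includes pre navitoclax (0h), and 2h, 4h, 6h, 8h post navitoclax draws on C1D14 and 24h draw on C1D15" and "Single pre-dose (pre-navitoclax) trough on C2D1". The Part 2 Schedule C calendar repeats the second of these.

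Section 2.5.1 states: "Pre-dose (0h) levels of trametinib and navitoclax will also be measured on day 1 of cycles 2, 4, 8 and 12". Its list of outputs includes "pre-dose (trough) drug concentration for trametinib and navitoclax, and t1/2". Sections 13.1.1.4 and 13.4.1.1 list Cmax, AUC(0-24), trough and t1/2, and they place the trough at the close of the dosing interval for both drugs. Neither section makes an exception for Schedule C.

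**The concern.** The sampling plan suits Schedules A and B. There, on PK days, trametinib is given one hour before navitoclax with an extra sample before it. Schedule C moves trametinib to the evening and stops it for half of each cycle, but the draws and the endpoint list were not adapted. Two listed trametinib endpoints, Cmax and trough, then no longer match what is sampled.

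Section 2.5.1 uses the concentrations to compare exposure at each combination dose level with single-agent exposure. Section 9.3.1.1 links them to the potential for efficacy, and Section 13.1.1 plans to correlate PK with toxicity. A Cmax that is biased low, or a washout level read as a trough, could be taken as reduced trametinib exposure in the combination. Section 5.1.1 closes further escalation on Schedules A and B from Protocol Version 10, so this concerns the schedule left for escalation.

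**Working it through.** **Inputs.** From Section 2.2.1.2, at 2 mg daily: median Tmax 1.5 h (single dose), effective half-life about 4.5 days (108 h), peak:trough about 2, accumulation ratio 6.6, and day-15 AUC(0-24) 376 ng·h/mL, Cmax 23 ng/mL and mean troughs 10.0-18.9 ng/mL. The documents give only a.m. and p.m. I assume a 12 h gap from evening trametinib to morning navitoclax and show 9-16 h.

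**Consistency of the cited figures.** The plan gives no figure on this point to reproduce. A 4.5-day half-life implies accumulation of 1/(1 − 2^(−1/4.5)) = 7.0 against the cited 6.6, which is close enough.

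**Where the serial draws fall.**
- Schedule C, 12 h gap: the 0, 2, 4, 6 and 8 h draws fall 12, 14, 16, 18 and 20 h after trametinib. The next-morning draw falls 12 h after the next dose.
- Schedules A/B: draws fall 0, 1, 3, 5, 7, 9 and 24 h after trametinib, so they bracket 1.5 h.
- With a Schedule C gap above 16 h, the 8 h draw passes 24 h and could follow that evening's dose.

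**Highest observed level as a fraction of peak (12 h gap).**
- Pure 4.5-day decay from Tmax: 2^(−10.5/108) = 0.93. This is an upper limit, because over 22.5 h it gives peak:trough of 1/2^(−22.5/108) = 1.16, not about 2.
- Log-linear fall from peak to trough with ratio 2: 2^(−10.5/22.5) = 0.72.
- Illustrative two-exponential profile with first-order absorption (assumed, ka 1.5-4 per h), fitted to the cited Cmax, AUC and half-life and a 10-14 ng/mL trough, then superposed: C1D14 0.60-0.65 (0.54-0.74 over 9-16 h); C1D7 0.52-0.64 (0.48-0.72).
- Floor: if the whole fall happens early, 1/2 = 0.5.
- For orientation, the cited average over peak is (376/24)/23 = 0.68.

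Under the same assumed profile, a trapezoid AUC(0-24) over these draws is 0.83-0.93 of true on C1D14 at 12 h.

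**Day-1 samples.** From the day-14 evening dose to the day-29 morning is 14.5 days, which is 13.5 days beyond a 24 h trough:
- 2^(−13.5/4.5) = 0.125. A gap of 9 h gives 0.127 and 16 h gives 0.122, so clock time hardly matters.
- An assumed half-life of 3.5 or 5.5 days gives 0.069 or 0.182.
- The ±3 day window in Section 10 applies after C2D1. It gives 2^(−10.5/4.5) = 0.198 to 2^(−16.5/4.5) = 0.079, if trametinib has not restarted.
- Scaled to the cited troughs: 0.125 × 10.0 to 0.125 × 18.9 = 1.25 to 2.4 ng/mL.

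**What the samples can support.**
- Near-trough: at a 12 h gap the C1D14 8 h draw is 20 h after trametinib. It is 2^(4/108) = 1.03 to 2^(4/22.5) = 1.13 times the 24 h trough on the simple bounds, and up to 1.15 on the assumed profile. At a 9 h gap it is up to 1.28 on that profile.
- Half-life: the C1D15 and C2D1 mornings are 14 days apart with no trametinib between them. The expected ratio is 2^(−14/4.5) = 0.116, which is informative for t1/2.

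**Text against text.** Sections 5.1.3 and 9.3.1.2 item (2) describe trametinib taken an hour before navitoclax on PK days, item (2) specifying the morning. The Schedule C footnote says evening, unadjusted. The Part 2 draw is tied to trametinib in 9.3.1.2.4 but to navitoclax in Appendix C and the Part 2 Schedule C calendar.

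**The case against.** The best case against runs as follows. These are descriptive secondary endpoints with no test or decision rule attached. The peak:trough ratio is only about 2, and cited between-subject variability is 27-50% for Cmax and 20-41% for AUC. The lower peak fractions come from an absorption model that the documents do not supply. Day 1 is literally pre-dose, and in a 14-on, 14-off regimen it is close to the regimen's minimum. Sampling details may also sit in a laboratory manual that is not shown.

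Much of this stands on size. The narrow modelled bands should not be quoted as findings, so only the wide range is used here. Variability is not an answer to direction, however: random spread averages out, while a timing bias shifts every patient the same way. The label defence fails on the endpoint sections, which place the trough at the end of the dosing interval; a level two weeks after the last dose is not that.

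The day-1 sample also has real value. It is a sound navitoclax trough and useful for trametinib t1/2, so it should be relabelled and kept.

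**Conclusion.** The point holds for Schedule C trametinib PK. Observed Cmax will understate the peak unless a late draw happens to follow the evening dose. The size depends on the model and on clock times that are not stated: about 0.6-0.9 of peak at an assumed 12 h gap, with a floor near 0.5. The trough mismatch is larger and firmer: about 12-13% of a 24 h trough at the cited half-life, or about 8-20% where the visit window applies and trametinib has not restarted.

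A reader might infer more, and the documents do not support it:
- That Schedule C values will be pooled with Schedule A/B troughs. No section says so; the fix only rules it out.
- That dose decisions or the interaction assessment are compromised. The DLT rules and the two-stage design use no PK, and the comparison singled out in 13.4.1.1 is navitoclax at levels 1A and 2A. Navitoclax PK and Schedule A/B PK are unaffected.
- That the Part 2 labels are a serious conflict. Under Schedule C one morning sample can precede both drugs, and Part 2 lists no PK endpoint. This is minor drafting.

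**What to change.** 1. In 13.1.1.4 and 13.4.1.1, state that trametinib Cmax is not reported for Schedule C from these draws. Report AUC(0-24) only as approximate or model-based, using recorded sample times and actual time since the last trametinib dose. Appendix C already requires sample times. Section 5.1 requires a diary of each dose; confirm that it captures clock times, since its form is not shown.
2. In 9.3.1.2.3, Section 10 and Appendix C, label the Schedule C day-1 samples of cycles 2, 4, 8 and 12 as trametinib washout levels and keep the navitoclax trough label. Do not summarise them as trametinib troughs or combine them with Schedule A/B troughs. Use them with C1D15 to inform trametinib t1/2.
3. Take as the near-trough trametinib level the last C1D14 draw confirmed to precede that evening's trametinib dose (usually the 8 h draw). Exclude any post-dose sample, and state that the value may read up to about 28% above the 24 h trough if the gap is short.
4. Reconcile the PK-day timing text in 5.1.3 and 9.3.1.2 item (2) with the Schedule C footnote. As a minor point, align the Part 2 draw label in 9.3.1.2.4 with Appendix C and the Part 2 Schedule C calendar.

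The cost is wording, with no added samples or visits. The downside is that fewer trametinib PK parameters are claimed under Schedule C.
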